5.5 Study Evaluations

- All subjects will be evaluated for photosensitivity (20 minutes with fluence of 106.7 J/cm² of HF-LED-RL) prior to start of study procedures, as recommended by the manufacturer's user guide instructions. A 20-minute session of HF-LED-RL phototherapy will be performed on the subject's nondominant proximal anterior forearm, and evaluation for photosensitivity will occur 24 hours post HF-LED-RL phototherapy. Subjects will be excluded from the study if they fail the 20 minute photosensitivity evaluation or do not return for photosensitivity evaluation between 24-48 hours post HF-LED-RL photosensitivity testing. Criteria for failing the photosensitivity testing include but are not limited to: warmth, erythema (redness), edema (swelling), rash, pain, or discomfort lasting more than 24 hours. Subjects are required to complete a study diary and report any adverse events to [name], [name], or [name].

5.6 Data Analysis

- Once all study subjects have finished all study procedures and data collection is complete, [name], [name], and/or [name] will then be performing the data analysis. Data analysis will include analysis of demographics (e.g. age, gender, ethnicity, race, Fitzpatrick skin type) in each cohort by HF-LED-RL or mock therapy dose, frequency of adverse events by HF-LED-RL or mock therapy

groups, mean duration of erythema, total duration of erythema, and subgroup analysis by demographics of adverse events. Self-reported outcomes of erythema duration are based on self-reporting from subject's diary.

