- This Phase 1 study (Storer 1989 – Phase 1 study design) will establish the safety of HF-LED-RL up to 640 J/cm² in human skin in this population of Fitzpatrick skin types I, II, and III. The results of this phase I study may establish differential safety of HF-LED-RL in Fitzpatrick skin types, which would determine dose stratification and treatment parameters for future clinical studies that use HF-LED-RL as a therapeutic modality. It may also determine what dose of HF-LED-RL is safe to use in Fitzpatrick skin types I

to III. Upon successful demonstration of safety of HF-LED-RL in Fitzpatrick skin types I to III, future phase II studies may reference our phase I safety data to perform efficacy studies of HF-LED-RL in human skin for treatment of skin diseases. The uniqueness and importance of our study for medical science is that this will be the first study of HF-LED-RL in humans with Fitzpatrick skin types I to III to evaluate the safety and regimen of these doses (480 and 640 J/cm²). Evaluating safety of HF-LED-RL phototherapy is important as HF-LED-RL may have the potential to treat skin diseases. To our knowledge, no clinical trials have been performed to determine the safety of HF-LED-RL in Fitzpatrick skin types I to III. Therefore, the innovation of this approach is that we intend to study the safety of HF-LED-RL modality in Fitzpatrick skin types I to III.

- This randomized, controlled Phase 1 clinical study requires a study temperature-matched control, which is the mock therapy device. The mock therapy will serve as a control and help evaluate if side effects are due to HF-LED-RL light or the heat output that is emitted from the study device. If an adverse event occurs with the HF-LED-RL device only, then the HF-LED-RL light may have caused the adverse event. If an adverse event occurs with the mock device only, then the adverse event may have been caused by the heat output. However, if the same adverse event occurs with both HF-LED-RL and mock therapy at the same time duration, then the adverse event may have been caused by the heat output generated from both HF-LED-RL and mock devices.

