3.0 Objectives

- The purpose of this study is to determine the safety of HF-LED-RL phototherapy in Fitzpatrick skin types I to III.
- We hypothesize that HF-LED-RL phototherapy at fluences of 480 J/cm² may be safe in subjects with Fitzpatrick skin types I to III. We hypothesize that HF-LED-RL phototherapy at fluence of 640 J/cm² may be safe in subjects with Fitzpatrick skin types I to III.

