After either a MTD has been established or the study endpoint of 640 J/cm2 has been achieved, an additional 27 HF-LED-RL phototherapy subjects (for a total of 30 or 33) and 18 mock therapy (for a total of 20 or 22) (determined randomly) will be enrolled to satisfy Hanley's Rule of Three, such that it can be concluded with 95% confidence that fewer than 1 person in 10 will experience an adverse event (Figure 3). (Hanley 1983) If the MTD is 320 J/cm2, then the study will be stopped and no further testing of the MTD of 320 J/cm2 in the larger cohort will be indicated because the MTD of 320 J/cm2 was already tested in a large cohort in the "previous Phase 1 LED-RL study". Of the larger expansion cohort, the study will be halted (stopped) if adverse events determined to be device related equals or exceeds 30%.

This clinical trial will be registered on <https://clinicaltrials.gov> following IRB approval and prior to subject enrollment.

- The subject will receive standard of care treatment in the dermatology clinic for any adverse event. Physical examination/visual inspection of the treated forearm will occur at every study visit. Treatment will be initiated, if indicated, for any procedural outcomes or adverse events noted at every study visit. Any general dermatology adverse events will be managed by [name] in the Dermatology clinic, per standard of care. If a skin ulcer occurs, we will record the skin ulceration as a superficial ulceration

(meaning it is nearly flush with the skin) or, if measurable, the depth of ulceration in millimeters. If skin ulceration occurs, we will consult [name], who is an expert in wound healing and head of the Sacramento VA wound clinic, for management. If change in sensation or muscle weakness occurs in a subject, the subject will be sent to Sacramento VA Emergency Room for urgent grading and management. If there are any other adverse events that cannot be managed in the Dermatology clinic, the subject will be sent to the Sacramento VA Emergency Room for urgent care.

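### Section 5.6 does not say that adverse events will be tabulated by dose received, so the planned table may not use the same-dose denominator behind the 1-in-10 statement

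*Combined protocol and SAP*

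**What the plan says.** Section 5.6 is the only analysis plan. One sentence covers first demographics and then the safety outcome: "in each cohort by HF-LED-RL or mock therapy dose, frequency of adverse events by HF-LED-RL or mock therapy". The noun that closes this phrase is groups, and 5.6 does not define it. Nor does it give a denominator, interval or analysis set for the main safety conclusion.

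That conclusion is set out in 5.1. After escalation, the trial enrols "an additional 27 HF-LED-RL phototherapy subjects (for a total of 30 or 33) and 18 mock therapy (for a total of 20 or 22"). The authors give the reason for these numbers as "to satisfy Hanley's Rule of Three". The claim that the numbers are meant to support is worded "such that it can be concluded with 95% confidence that fewer than 1 person in 10 will experience an adverse event". The Abstract adds a total of 50 subjects for this step, which is 30 + 20: one escalation cohort plus the expansion cohort.

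Section 3.0 states a separate hypothesis for each dose, for instance "We hypothesize that HF-LED-RL phototherapy at fluence of 640 J/cm² may be safe". Section 2.0 separates light from heat by asking "if the same adverse event occurs with both HF-LED-RL and mock therapy at the same time duration". Section 5.1 sets that duration at 90 minutes for 480 J/cm² and 120 minutes for 640 J/cm².

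**The concern.** Safety at each dose is the trial's only objective, yet the sentence that plans the safety table leaves dose out after naming it for demographics. Read most naturally, as HF-LED-RL versus mock, the table pools two doses. A pooled percentage answers neither hypothesis in 3.0, and its denominator is not the one from which 5.1 draws its conclusion. It also pools mock sessions of different length, although the reasoning in 2.0 compares like durations.

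At stake is which fraction is reported as the trial's result. Under 5.1 the researchers know every subject's allocation, and under 5.6 the analysis comes after data collection. A denominator left open would then be chosen with the results in view.

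**Working it through.** **Inputs (5.1).** Group 1 (480 J/cm²): 3 or 6 HF-LED-RL subjects. Group 2 (640 J/cm²): 3 or 6. Group 3 (one selected dose): 27. The study stops if the MTD is 320 J/cm², so Group 3 opens only after both doses have been given.

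**Formula.** The exact one-sided 95% upper limit for 0 events in n is 1 − 0.05^(1/n). For x events it is the 0.95 quantile of Beta(x + 1, n − x).

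**The plan's own figure.** Rule of three: 3/30 = 0.100. Exact: 1 − 0.05^(1/30) = 0.0950, and for n = 33, 0.0868. The smallest n with 0.9^n ≤ 0.05 is 29. The stated 30 or 33 is therefore reproduced as a one-sided, zero-event statement.

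**Denominators with Group 3 at 27**

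| Group 1 | Group 2 | At 480 if expanded | At 640 if expanded | Whole HF-LED-RL arm |
|---|---|---|---|---|
| 3 | 3 | 30 | 30 | 33 |
| 3 | 6 | 30 | 33 | 36 |
| 6 | 3 | 33 | 30 | 36 |
| 6 | 6 | 33 | 33 | 39 |

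The same-dose total is 30 or 33 in every path, as 5.1 states. The arm total is never 30 and always mixes doses. The pooled 3 + 3 + 27 = 33 equals the stated 33 (6 + 27) only by coincidence: 30 of those 33 share a dose. The mock arm has the same trap: 2 + 2 + 18 = 22 equals 4 + 18 = 22.

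**Example.** Suppose Group 1 is event-free, 640 J/cm² is rejected after events in 2 of 3 HF-LED-RL subjects, and 480 J/cm² is expanded without an event.

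- By dose: 480 is 0/30, limit 9.5%, so the 1-in-10 statement holds; 640 is 2/3 = 67%.
- By arm: 2/33 = 6.1%, limit 17.9%, so the statement appears to fail.

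**Numbered-cohort reading.** The rows are 3 or 6, 3 or 6, and 27. The needed 30 or 33 is the Group 3 row plus the escalation row at the same dose.

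**Effect of the default rule in 5.1.** The randomization text moves the five unused subjects of an event-free Group 1 or 2 into Group 3. Assuming the 3:2 split is kept, that adds 3 HF-LED-RL subjects per such group. Group 3 becomes 27, 30 or 33, and the same-dose total 33 or 36. The arm total becomes 39, or 36 if Group 2 stops early and its spare places go unused. In the example, the figures become 0/33 (8.7%) by dose and 2/36 (16.5%) by arm, so the contrast remains.

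**The case against.** The strongest reply is that groups need not mean arms. In 5.1 the word denotes the numbered cohorts, each of which has one dose, and the opening reference to cohorts in the 5.6 list could govern the whole list. On either reading adverse events are already split by dose, and 5.1 already gives the intended 30 or 33. This stands in part. It shows that the information is not lost, but not that 5.6 says which rows to combine.

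A second reply is that 5.6 plans no interval at all, so the 17.9% is a limit that nobody proposed to compute. That is true. But the 1-in-10 statement is itself an upper limit, and some count must go into it.

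Four stronger readings are tempting and are not supported:

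- *No reading of the table yields 30 or 33.* Two cohort rows add to it, and under the default rule (3:2 kept) Group 3 alone can reach it.
- *A cohort table misses 10% even with no event.* Group 3 alone at 0/27 does give 10.5%, but nothing in the documents draws the conclusion from Group 3 alone.
- *Pooling would produce a false claim of safety at 640 J/cm².* If 640 is expanded with no event and both escalation cohorts stay at 3, pooling gives 0/33 (8.7%) and the same-dose count 0/30 (9.5%). Both are below 10%.
- *Pooling would hide the toxicity of a rejected dose.* Events in two or more subjects are what reject a dose under 5.1, so they would be declared through the dose-finding rule whatever 5.6 tabulates.

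**Conclusion.** The point holds as a defect of specification. Section 5.6 does not commit to adverse-event frequency by dose received. On the arm reading it mixes doses in every path that reaches expansion (33, 36 or 39 subjects against a same-dose 30 or 33), and it can turn a limit of 9.5% into 17.9%. On the cohort reading it leaves the key addition unstated.

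The figures assume Group 3 at its listed 27; with the default rule they shift as shown, but the conclusion does not. The example is illustrative, and its probability was not estimated. The damage is limited: subject-level data would allow the right table at any time, and 5.1 states the intended totals. The reason to act now is to fix the denominator before results are seen.

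**What to change.** Replace the adverse-event phrase in 5.6 with text to this effect:

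> The number and percentage of subjects with at least one adverse event will be given by dose level received (480 or 640 J/cm²) and arm. Group 3 will be combined with the escalation cohort or cohorts treated at the same dose. Exact one-sided 95% upper limits will be shown. The 1-in-10 conclusion refers only to HF-LED-RL subjects at the expanded dose and will be drawn only if that limit is below 10%.

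The last condition matters because the 33 path arises only after an adverse event at that dose. If that event was in an HF-LED-RL subject, 1/33 gives a limit of 13.6%.

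Mock subjects may be listed by session duration (90 or 120 minutes), descriptively only: with the listed sizes, the non-expanded duration has 2 or 4 of them.

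Within 5.1, reconcile the listed Group 3 size (27 + 18 = 45) with the rule that moves unused Group 1 and 2 subjects into it, because that changes the denominator.

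The cost is a few sentences, with no new subjects or data. The downside is that the non-expanded dose will carry a very wide limit (63% for 0/3, 39% for 0/6), which is a fair picture of what the trial can say about it.

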5.7 Withdrawal of Subjects

- Subjects may be withdrawn from the research without their consent in the event of an adverse event that jeopardizes the subject's safety or subject's noncompliance (e.g. missing two or more study visits). In the event that subject's study participation has to be discontinued, the principal investigator will explain to the participant the reasons for termination.
- There are no consequences/penalties should a subject decide to withdraw from the research. The subject is encouraged to contact [name] for the end-of-study visit. End-of-study visit will include photograph of the treated forearm, physical examination of the treated forearm, and collection of the subject's study diary. Subjects will be instructed to notify their primary care physician or follow-up in Dermatology clinic if any questions or concerns arise after the end of the study.

6.0 Reporting

- All subjects will be seen by [name] (Principal Investigator), [name], or [name]. Study subjects are followed by their regular physicians, so

they will continue to receive usual care. [name], [name], or [name] will review the study subject's safety parameters (including history and physical) after study enrollment.

Although this is a minimal risk study, [name], [name], or [name] will monitor study subjects for common expected procedure outcomes and adverse events during and immediately after HF-LED-RL phototherapy or mock therapy. Monitoring will occur by direct observation and review of subject diary of adverse events at all study visits.

[name] (Principal Investigator) will promptly report any serious adverse events or unanticipated problems involving risks to study subjects in accordance with regulations: reportable adverse events arising from any of the study procedures will be submitted promptly to the IRB. Although they are not anticipated to occur, unanticipated problems (involving risks to subjects) or Serious Adverse Events (SAE) in subjects will be reported to the IRB within 5 working days of awareness of the event. Copies of reports should be received by the IRB no later than 15 calendar days after the event.

- Performance and Frequency of Safety Reviews

[name] (Principal Investigator) reports on the progress of the study on a quarterly basis at the DSMB meeting. [name] (Principal Investigator) will monitor study progress, outcomes and subject safety, and may make recommendations on changes to the study protocol. Meetings regarding the performance and safety of this study will be held quarterly at the Dermatology Clinic Conference room. The DSMB will report to the IRB quarterly.

- Individuals who will perform the safety monitoring

[name] (Chief, Dermatology Service)

[name] (Chairperson, UC Davis Dermatology)

[name] (Associate Professor, UC Davis Dermatology)

8.0 Communication Plan

- N/A

